**Table 9: Schedule of Procedures for Experimental Sessions**

Approximate Time	Procedure or Action
8:30	Urine drug screen and pregnancy test, concomitant medication information collected, self-reported measures and C-SSRS administered, participant acclimated to environment
8:55	Baseline BP, body temperature, pulse
9:00	IMP Administration , Begin video recording
10:30	BP, body temperature pulse Supplemental Dose Administration , unless tolerability issues emerge with the first dose or it is refused by the participant
16:30	C-SSRS, BP, body temperature, pulse

*Pre-IMP Administration*

- 24 to 48 hours prior to the first Experimental Session, the participant will be randomized.
- On the day of the Experimental Session, the participant will arrive approximately 30 to 60 minutes prior to IMP administration.
- The therapy pair will direct the participant to complete the PCL-5 and BDI-II and will administer the C-SSRS.
- The site team will ensure the participant has not used caffeine or nicotine 2 hours prior and has fasted for 10 hours prior to IMP administration and complied with all other requirements per [Section 3.3 Lifestyle Modifications](#).
- The site team will inquire about any possible changes in health to ensure the participant continues to meet all eligibility requirements and record AEs as described in [Section 10.0 Safety](#).
- The site team will instruct the participant that they will not be able to use caffeine or nicotine at least 6 hours after the IMP administration.
- The site team will complete urine drug screen, pregnancy test, and concomitant medication review.
  - A positive drug screen will be reviewed by the site physician and may be cause for delaying IMP administration to a later time, rescheduling the session to a later date, or withdrawing the participant from the study, based on Medical Monitor review.
  - A positive pregnancy screen is cause for withdrawal from the protocol.
- The therapy pair will review procedures for the Experimental Session with the participant and discuss the participant's goals, intentions, and concerns and some of the commonly experienced effects of MDMA.
- If the participant continues to be eligible, the session will proceed.
- Baseline blood pressure, body temperature, and pulse will be measured just prior to administration of the initial dose.

*During the Experimental Session*

- After video recording has begun, at approximately 9:00 in the morning, a qualified staff member will administer the initial dose of IMP with an electrolyte-containing fluid. The participant will sit or recline on comfortable furnishings. Eyeshades and a program of music will be provided for the participant if they wish to use them. Whenever they wish, participants may speak to the therapy pair, who will provide guidance and support, as needed.
- After the first hour, if the participant has not spoken spontaneously, the therapy pair will check in with them about the nature of the experience. For the rest of the experience, as appropriate, the therapy pair will support and encourage the participant in emotional

processing and resolution of whatever psychological material is emerging, as described in the Treatment Manual.

- Water or Electrolyte-containing fluids will be provided throughout the session but not to exceed three liters overall.
- Blood pressure, body temperature, and pulse will be measured approximately 1.5 to 2 hours after the initial dose, before the supplemental dose is administered.
- If the participant prefers not to have the supplemental dose, the therapy pair will document the reason.
- The site physician will be contacted with a brief description of how the session is progressing and the recent vital signs. The site physician will approve or deny the administration of the supplemental dose. If an AE requiring medical attention has occurred between the initial and supplemental dose, the site physician will determine whether the supplemental dose is recommended or not. If medical attention is needed, the site physician will provide further instruction or consult the Medical Monitor.
- A supplemental dose will be administered with a glass of electrolyte-containing fluid approximately 1.5 to 2 hours after the initial dose, unless tolerability issues emerge with the first dose or it is refused by the participant.
- Food will be provided during the latter part of the session.
- If there is an approved companion, that person may arrive as agreed upon but will wait in the waiting room until a member of the therapy pair brings them to the session room. Alternatively, the companion may arrive after the session has ended.

#### *End of Experimental Session*

- The therapy pair will record AEs and concomitant medications.
- Blood pressure, body temperature, and pulse will be measured approximately 8 hours after the initial dose.
- The therapy pair will administer the C-SSRS.
- The session may be ended if all medical and psychiatric parameters are acceptable, elevations in vital signs have resolved to pre-IMP levels, the participant is alert, ambulatory, and emotionally stable, and the night attendant has arrived.
- The therapy pair or site physician shall remain available to participants via 24-hour cellular phone for support, as needed.

#### *Overnight Stay*

- The participant will remain overnight with the therapy pair or a night attendant in accordance with site SOPs.
- Participants will remain overnight in an appropriately furnished room at or near the study site until after the Integrative Session the morning after each Experimental Session. With prior approval of the therapy pair, a companion may accompany the participant during the overnight stay.
- An attendant will check in periodically on the participant during the overnight stay, even if a companion is present. The attendant will monitor participant condition and will help participants relax during the overnight stay. The attendant will be an individual with some previous training in caregiving and will be supportive but not intrusive. If there is an emergency or the participant needs additional support, the attendant can contact the therapy pair.
- The participant and a companion (if applicable) will receive information that will allow them to contact the therapy pair during the overnight stay in the case of an emergency or to request additional support.
- Participants will be encouraged to use much of the time during their overnight stay for rest and as a period of reflection and integration in a quiet atmosphere.

- Participants may not drive until after the Integrative Session and cleared by therapist, as emotional processing may impair their attention and focus.

### **7.3.2 Telephone Contact After Experimental Sessions**

The goal of the telephone contact is to assess health changes, ensure participant safety, and offer support. A member of the therapy pair will follow-up with the participant by telephone on every other day for 14 days after each Experimental Session (starting 2 days post-Experimental session). Each call will last on average five to 15 minutes but could be longer to address participant concerns and to adequately assess wellbeing. Additional telephone contact can be initiated at the request of the therapy pair or participant.

At each telephone contact, the member of the therapy pair will:

- Inquire about any possible changes in health, assess the participant's mental health and the status of any previously recorded Aes, and record Aes as described in [Section 10.0 Safety](#).
- Inquire about concomitant medication use and adherence.
- Offer support in accordance with the Treatment Manual.
- Administer the Since Last Visit C-SSRS.

### **7.3.3 Integrative Sessions**

After each Experimental Session, three Integrative Sessions will take place. Each session will consist of 90 minutes of therapy.

#### *Treatment 1*

- Integrative Session 1.1 (Visit 6): morning after Experimental Session 1 (Visit 5).
- Integrative Session 1.2 (Visit 7): ~1 week (3 to 14 days) after Experimental Session 1 (Visit 5).
- Integrative Session 1.3 (Visit 8): ~2 weeks (10 to 21 days) after Experimental Session 1 (Visit 5). This visit serves two purposes: to continue integration and to prepare for the next Experimental Session.

#### *Treatment 2*

- Integrative Session 2.1 (Visit 10): morning after Experimental Session 2 (Visit 9).
- Integrative Session 2.2 (Visit 11): ~1 week (3 to 14 days) after Experimental Session 2 (Visit 9).
- Integrative Session 2.3 (Visit 12): ~2 weeks (10 to 21 days) after Experimental Session 2 (Visit 9). This visit serves two purposes: to continue integration and to prepare participants in Group 1 (3-Session Group) for the next Experimental Session.

#### *Treatment 3 (3-Session Group only)*

- Integrative Session 3.1 (Visit 14): morning after Experimental Session 3 (Visit 13).
- Integrative Session 3.2 (Visit 15): ~1 week (3 to 14 days) after Experimental Session 3 (Visit 13).
- Integrative Session 3.3 (Visit 16): ~2 weeks (10 to 21 days) after Experimental Session 3 (Visit 13). This visit will be the final Integrative Session prior to entering the Post-Treatment Period.

During Integrative Sessions, the therapy pair will:

- Record the session.

- Inquire about any possible changes in health. Assess the participant's mental health and the status of any previously recorded AEs. Record AEs as described in [Section 10.0 Safety](#).
- Inquire about concomitant medication use and adherence.
- Discuss and review events that occurred with the participant during the Experimental Session, including thoughts, feelings, and memories. If necessary, the therapy pair will help the participant to reduce any residual psychological distress they are experiencing. The therapy pairs will also encourage the transfer of states of acceptance, feelings of intimacy, closeness, and reduced fear experienced in Experimental Sessions to emotionally threatening everyday situations. The therapy pairs will be supportive, validate the experience, and facilitate understanding and emotional clearing.
- Be accessible for additional support via phone or telemedicine if needed.

## 7.4 Post-treatment Period and Study Termination

### 7.4.1 Post-treatment Period

After the last Integrative Session, participants will enter follow-up for approximately 4 weeks with no protocol required visits until the Outcome CAPS-5 T2 assessment. This assessment will also include the SDS and the DSP-I. Participants will have access to therapy pairs for support if needed, and additional visits via phone, telemedicine, or in person can be scheduled if requested. Participants will continue to comply with protocol requirements for concomitant medications until after Study Termination.

Participants will be scheduled for an in-person visit within 1 to 7 days after the CAPS-5 T2, where qualified site staff will arrange the post-treatment blood draw, administer the MAPS-Adapted C-SSRS (Since Last Visit), and actively support participants in the completion of the self-reported outcome measures.

- WHOQOL-BREF
- AAQ-II
- SCS
- BPAQ-SF
- PCL-5
- MIES
- BDI-II
- CPGS
- PTGI
- UFEC
- AUDIT
- DUDIT

Participants in the two Experimental Session group will have a second outcome evaluation (T2.2, Visit 15) timed to be concurrent with those who completed three Experimental Sessions, approximately 4 weeks after their first post-treatment assessment at T2 (Visit 13). A blinded IR from the IR Pool will conduct the assessments via telemedicine. These assessments may be recorded to establish inter-rater reliability. Participants will be instructed to withhold from sharing with the IRs their progress in the study including how many visits or Experimental Sessions they have had.

Participants who have withdrawn from treatment will also complete a final CAPS-5 assessment immediately upon withdrawal. The IR will also administer the DSP-I and the SDS.

Following post treatment assessment, participants will engage in post treatment planning with the treatment team and are no longer required to comply with requirements related to concomitant medication or other forms of therapy.

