## 4.2 Study Design Overview

This open-label, randomized Phase 2 study will assess the relative safety and effectiveness of two versus three Experimental Sessions of MDMA-assisted therapy in treatment-seeking veterans diagnosed with PTSD.

[figure not shown]
The study will be conducted in up to 60 participants. Randomization will occur in a 1:1 fashion and will be allocated to Group 1: 3 Experimental Sessions of MDMA-assisted therapy or Group 2: 2 Experimental Sessions of MDMA-assisted therapy.

For each participant, the study will consist of:

[figure not shown]
- **Screening Period (~4 weeks):** Phone or in person screen, informed consent, eligibility, and baseline assessment
- **Preparatory Period with Enrollment Confirmation (at least 7 days, max time dependent upon medication tapering):** medication tapering, Preparatory Sessions and Baseline assessments leading to Enrollment Confirmation.
- **Study Enrollment and Randomization:** Include eligible participants, randomize to group, complete baseline self-report measures, collection of pre-treatment biomarker blood samples
- **Treatment Period (Group 1: 9-15 weeks, Group 2: 6-10 weeks):** Each Experimental Session followed by 3 non-drug Integrative Sessions.
- **Post-treatment (~4 weeks):** At one-month post final Integrative Session, clinical evaluation and self- report measures, collection of post-treatment biomarker blood samples.
  - For the 2-session group: additional clinical evaluation one month following post-treatment as a secondary outcome.
- **Study Termination:** After the Study Termination visit, participants will have the opportunity to enroll in a separate LTFU study at least six months from the final Experimental Session.

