**Table 1: CAPS-5 Data Collection by Visit**

CAPS Number	Visit	Description/Timing	Target Timing Post Baseline
Baseline CAPS-5 T1	V3	Baseline between Visits 2 and 4 (Preparatory Sessions), after medications have been tapered.	Not Applicable
CAPS-5 T2	V13 (2-session group) or V17 (3-session group)	Post Treatment Primary Outcome 49 to 56 days after last Experimental Session	63 to 98 days or 85 to 134 days
CAPS-5 T2.2	V15 (2-session group only)	Secondary outcome for 2-session group only 28 to 35 days after T2	85 to 134 days

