## **11.0 Concomitant Medications**

### **11.1 Tapering Instructions**

The site physician will record concomitant medications during Screening. If the prospective participant is being treated with psychiatric medications at enrollment, the prospective participant will be encouraged to discuss medication tapering with their outside treating physician, if any, and will be required to give the site physician permission to do so as well. Additionally, participants who are taking prohibited opiates will be cross-tapered to an allowable opiate (hydrocodone, morphine, and codeine) under the care of their prescribing physician.

The site physician will consult the prescribing physician to initiate medication tapering for participants, as they must refrain from taking psychiatric medications throughout the study, with some exceptions (see [Section 11.2 Allowed Concomitant Medications](#)). The prescribing physician's opinion about medication discontinuation will be documented either in writing from the prescribing physician, or in writing by the site physician documenting phone contact with the prescribing physician. Tapering will follow a time course appropriate for the medication based on its half-life, with the Baseline CAPS-5 T1 (Visit 3) scheduled to occur after complete washout for psychological medications and Experimental Session 1 (Visit 5) scheduled to occur after complete washout for medications with drug-drug interactions without a psychological concern (five half-lives plus at least 1 week for stabilization).

The therapy pair will request information about any changes in medication at each contact. The site physician will be responsible for reviewing and confirming all medications collected during the study.

All medications, non-prescription and prescription, will be collected from Screening through 7 days after the last Experimental Session. From 7 days after the last Experimental Session through Study Termination, only prescription or non-prescription medications taken to treat AEs will be collected. Throughout the protocol, all medications used to treat AEs will be collected, and all changes including discontinuations or additions to medications will be collected. The study team will also inquire about concomitant medication adherence and document all information on the Concomitant Medications eCRF.

Participants may return to taking psychiatric medications and discontinue contraception after the final Study Termination visit if necessary.

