## 11.3 Prohibited Medications

To be enrolled in the study, participants must:

- Refrain from the use of any psychoactive medication not approved by the research team from Baseline through Study Termination (with the exception of gabapentin or certain opiates for pain control).
- Be willing to comply with all medication requirements per protocol. Medications will only be discontinued after enrollment per clinical judgment of the site physician in consultation with the prescribing physician.
- Agree that, for 1 week preceding each Experimental Session they will refrain from:
  - Taking any specified herbal supplement (except with prior approval of the research team).
- Agree that, for 5 half-lives of the medication preceding each Experimental Session they will refrain from:

- Taking any nonprescription medications (with the exception of non-steroidal anti-inflammatory medications or acetaminophen) unless with prior approval of the research team.
- Taking any prescription medications (with the exception of birth control pills, thyroid hormones, or other medications approved by the research team).

Use of Marijuana, St. John's Wort, and other herbs and medicines with notable serotonergic effects are prohibited from Baseline to Study Termination. Any investigational treatments under study for PTSD treatment are prohibited from use concurrent with this study.

Diphenhydramine is excluded from this study unless prior approval is granted by the site physician.

If an SSRI, SNRI, MAOI, or other antidepressant is used between Experimental Session 1 (Visit 5) and Study Termination, the participant will be withdrawn from treatment and continue in follow-up.

Opiates other than hydrocodone, morphine, and codeine are prohibited from Enrollment Confirmation to Study Termination. Participants taking prohibited opiates will be cross-tapered to an allowable opiate during the Preparatory Period. Participants whose Experimental Sessions are delayed by the COVID-19 pandemic may start any of these medications during the delay, as clinically indicated. When study visits resume, they will be given the option to resume Experimental Sessions after tapering off of these medications, per the tapering plan described above.

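### Protocol 7.4.1 both keeps the medication requirements to Study Termination and lifts them after an undefined post-treatment assessment, which may leave T2.2, a 2-session-arm outcome only, unprotected

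*Protocol*

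**What the plan says.** **Requirement kept.** The first paragraph of Protocol 7.4.1 states: "Participants will continue to comply with protocol requirements for concomitant medications until after Study Termination". Section 11.3 bars unapproved psychoactive medication "from Baseline through Study Termination (with the exception of gabapentin or certain opiates for pain control", and 3.3 sets the same span. Section 11.1 permits a return to psychiatric medication only once the final Study Termination visit is over.

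**Requirement lifted.** The last paragraph of 7.4.1 reads: "Following post treatment assessment, participants will engage in post treatment planning with the treatment team", and adds that they "are no longer required to comply with requirements related to concomitant medication or other forms of therapy".

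**What post-treatment means.** Protocol Table 1 labels T2 the post-treatment primary outcome. Section 7.4.1 places T2.2 "approximately 4 weeks after their first post-treatment assessment at T2 (Visit 13". Section 4.2 says: "For the 2-session group: additional clinical evaluation one month following post-treatment as a secondary outcome". Table 1 describes T2.2 as "Secondary outcome for 2-session group only 28 to 35 days after T2".

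**Use of T2.2.** Protocol 13.2.3 planned an exploratory equivalence comparison of T2.2 in the 2-session arm with T2 in the 3-session arm. After early termination, SAP 7.7.1 and 7.7.2 report CAPS-5 and SDS at T2.2 descriptively, with 95% confidence intervals.

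**Recording.** Section 11.1 says that, starting a week after the final Experimental Session, "only prescription or non-prescription medications taken to treat AEs will be collected". Its next sentence says that medication additions and discontinuations are collected throughout the protocol.

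**The concern.** A site cannot follow both sentences of 7.4.1. Whether a 2-session participant is still bound by the medication rules between T2 and T2.2 depends on which sentence the site applies, and different staff could apply different ones.

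The schedule makes the consequence one-sided. Only the 2-session arm has a CAPS-5 after T2. If the release starts at T2, the T2.2 score may reflect two sessions plus whatever medication was started in the following month, whereas the 3-session T2 with which it was to be compared was measured under restriction. T2.2 was the time-matched comparator, so this would confound the one comparison meant to remove the difference in time since baseline.

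The recording rule matters because a reader of the T2.2 interval needs to know how many participants had started other medication. If 11.1 is applied narrowly, that count could be incomplete.

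**Working it through.** The plan gives no figure for this point, so the check rests mainly on the text and the visit windows.

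**1. The two rules side by side**

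| Place | Medication requirements end |
|---|---|
| 7.4.1, first paragraph | after Study Termination |
| 3.3 and 11.3 (psychoactive medication) | Study Termination |
| 11.1 (return to psychiatric medication) | after the final Study Termination visit |
| 7.4.1, last paragraph | after the post-treatment assessment, no visit named |

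**2. Length of the disputed window in the 2-session arm**

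- Release at T2 (Visit 13): T2.2 follows 28 to 35 days later (Table 1).
- Release at the outcome site visit (Visit 14, 1 to 7 days after Visit 13, Table 6): 28 − 7 = 21 to 35 − 1 = 34 days.
- Release after the last CAPS-5 (Visit 15): T2.2 is not exposed. The conflict is then confined to the 1 to 7 days before Study Termination (7.4.2), with no CAPS-5 in them.

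The CAPS-5 rates the last month (6.1.1), so the first window covers about the whole T2.2 look-back.

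**3. The 3-session arm.** By Table 5, Visit 19 falls 1 + 0 = 1 to 7 + 7 = 14 days after T2. No CAPS-5 is scheduled there, so an early release cannot alter that arm's outcome.

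**4. Recording.** T2 is 49 to 56 days after the last Experimental Session (Table 1). The narrower rule therefore starts 49 − 7 = 42 to 56 − 7 = 49 days before T2, in both arms.

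**5. Illustrative size.** The documents give neither a rate of starting other treatment nor its effect. Assume a fraction f of 10% to 30% and an improvement e of 5 to 10 CAPS-5 points each. Shift in the T2.2 mean = f × e:

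- low: 0.10 × 5 = 0.5 points
- high: 0.30 × 10 = 3.0 points

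**6. What that would have meant for the planned exploratory comparison.** First, the planned sample size under 13.2.1 (margin 10, SD 11.5, each one-sided test at 5%, 90% power, true difference 0):

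n per arm = 2 × [11.5 × (1.645 + 1.645) / 10]² = 28.6, so 29. Exact t-based power at 30 per arm is 90.8%. The plan's 30 per arm is reproduced and is not in dispute.

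With the same inputs and a shift of 0.5 to 3.0 points in the T2.2 mean:

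- true difference 10, shift towards zero: the chance of declaring equivalence rises from 5% to between 7% and 26%
- true difference 0: power falls from 90.8% to between 90% and 75%

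**7. Current scale.** The SAP reports termination at about 20 participants, so roughly 10 per arm if 1:1 held (assumption). With SD 11.5 to 12.7 (the two values in Section 13), the 95% half-width for a mean change is 2.262 × 11.5 / √10 = 8.2 to 2.262 × 12.7 / √10 = 9.1 points. One participant is about 10% of the arm mean.

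**The case against.** The strongest reply is that the release sentence closes 7.4.1, after the T2.2 paragraph, and is linked to planning for after treatment. The only plan the protocol defines, the Post-Study Plan, is given at Study Termination (7.4.2 and 7.4.3). Read that way, the release follows the last CAPS-5 and T2.2 is protected. This reading is possible, so the unrestricted days cannot be stated as fact. It still conflicts with the first paragraph, and the protocol's own labels make T2 an equally natural trigger.

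A reader might go further and infer that medication restarts could be neither detected nor analysed. The documents do not support that. The second 11.1 sentence covers additions, and a restart is an addition. Table 6 schedules a medication review at Visits 14, 15 and 16. Section 13.2.4 tabulates psychiatric medication by period, including follow-up. Section 10.1 counts worsening of an existing condition as an AE, so a drug given for worsening PTSD would be captured even under the narrow rule. What stands is that the two 11.1 sentences disagree on what to enter, in both arms alike. SAP 7.8.3 also does not repeat the by-period split.

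A reader might also treat the release from therapy requirements as a second contradiction. The sentences that keep the rules to Study Termination concern medication. The commitment in 3.3 not to begin new mental healthcare covers the screening and treatment phases only. New therapy after treatment is therefore a gap, not a conflict, and it is not confined to one arm or to the time after T2.

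Finally, the stakes are limited: T2.2 against T2 was exploratory, and the SAP states that the reduced sample will not support efficacy conclusions. That is correct, and it bears on the weight of the point, not on whether the text conflicts.

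**Conclusion.** The contradiction in 7.4.1 is real and needs no assumption. That it reaches T2.2 depends on reading the post-treatment assessment as T2 or Visit 14, which the protocol's usage permits but does not settle. On that reading the exposure is up to 28 to 35 days (21 to 34 from Visit 14), in the 2-session arm only.

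The primary T2 comparison is not affected by this release. The effect on T2.2 is unknown. The 0.5 to 3.0 points rest wholly on the assumed 10% to 30% and 5 to 10 points, and are small beside a half-width of 8 to 9 points at about 10 participants. A larger shift, such as one built on half the arm restarting, has no basis in the documents. The error probabilities in the working apply to the comparison as planned at 30 per arm, which will not now be run.

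The 11.1 recording conflict is a separate, minor point, and is harmless if the second sentence governs.

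**What to change.** 1. **Protocol 7.4.1, with 3.3, 11.1 and 11.3.** Reconcile the passages so that one release point is stated by visit, relative to T2, T2.2 and Study Termination. Which point is right is for the sponsor and investigators to decide, not this review. State whether the release from therapy requirements has the same timing, since no cited rule now covers that period.
2. **Protocol 11.1.** Reconcile the two recording sentences so that it is clear that new psychiatric medications are entered through Study Termination, as the follow-up tabulation in 13.2.4 implies.
3. **SAP 7.7.1 and 7.7.2.** Report beside T2.2 the number of 2-session participants who started psychiatric medication between T2 and T2.2. Present it as a descriptive flag. An analysis excluding those participants is not advised: it would select on a post-randomisation event related to outcome, in about 10 people.

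Cost: wording changes in four protocol sections and one line in two SAP tables. Medication is already reviewed at the relevant visits, so no new visit is needed. With enrolment ended early, the protocol edits may have little prospective effect; the SAP line remains useful wherever the data were captured.
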